	
allowing the study to be stopped early for efficacy. A second interim analysis is planned at approximately, but no less than, 250 deaths, with a two-sided p-value ≤ 0.0151 allowing the study to be stopped early for efficacy.
 
A conditional power of less than or equal to 15% at each of the interim analyses will result in the study stopping early for futility.
 
Sample size modification will be considered at the second interim analysis following the approach described in Mehta & Pocock (2011)¹⁶ which employs an un-weighted test statistic at the final analysis as recommended by Burman & Sonneson (2006)¹⁷.
 
Final Analysis of primary endpoint: The final analysis, without a sample size modification, will be performed when approximately, but no less than, 417 deaths have occurred. A two-sided p-value ≤ 0.0363 is required to declare a statistically significant improvement in median OS at the final analysis.
 
If the sample size is increased after the second interim analysis, the final analysis will be performed when approximately, but no less than, 564 deaths have occurred, which will result in 80% power to detect an improvement in median OS from 10.7 to 13.7 months using a log rank test with a final two-sided alpha of 0.0363.
 
Analysis of secondary efficacy endpoints
 
Comparison between treatment groups for all secondary endpoints will be conducted at the final analysis with a two-sided alpha of 0.05.
 
Time to event endpoints (ie, TTP, TTUP, TTSP) will be compared between treatment arms using a log-rank test. Tumor response rates will be compared between treatment arms using the continuity adjusted Newcombe-Wilson test. The FACT-Hep score will be compared between treatment arms using a mixed linear model with baseline score and the relative time from baseline as covariates.
 
Safety Analysis: All patients who received study treatments at least once will be included in the safety analysis. All Adverse events (AEs) will be reported according to the National Cancer Institute Common Terminology Criteria for Adverse Events v 4.0 (CTCAE) grades and coded using the Medical Dictionary for Regulatory Activities (MedDRA). The incidence of treatment emergent adverse events (events which were not present at baseline or worsened in severity following the start of treatment) will be summarized according to MedDRA primary system-organ class (SOC) and preferred term (PT). Laboratory values will be summarized by treatment group over time and overall.
 
A feasibility safety assessment will be conducted after the first 20 patients in the treatment group have received both TS and sorafenib therapy.
 
Poolability and Other Analysis: Multivariate Cox regression analysis of time-to-event efficacy endpoints will be conducted on stratification criteria and other factors such as age, gender, duration of disease prior to randomization.
 
As a sensitivity analysis, to address the poolability of data across regions, study sites and gender, a Cox regression analysis of the primary efficacy endpoint, OS, will be conducted with factors of region, study site and gender, and to determine the impact of these factors on OS. Note: region and study site will not be included simultaneously in the model due to collinearity.
 
Should the impact of region, site or gender on OS be statistically and clinically relevant, the reasons for the observed differential treatment effect, such as patient

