- Quality of Life. The total score of FACT-Hep will be calculated, the scores of each domain and each question at each time-point and their differences from baseline will be summarized for each treatment group. The two treatment groups will be compared applying a mixed model repeated measures analysis with the treatment, visit and the interaction between treatment as factors, the baseline score as a covariate and further adjusted for the interaction between baseline and visit. A deterioration in QOL is defined as a 7-point decline in the total score or death whichever occurs first. The time to deterioration in QOL (TTDQoL) will be calculated as the interval between the randomization date and deterioration in QOL. The Kaplan-Meier method will be used to estimate the TTDQoL curves in the two treatment arms; comparison between the curves will be performed using the log-rank test

A detailed description of data censoring handling for patients will be defined in the Statistical Analysis Plan.

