8.6.3 Analysis of Quality of Life Questionnaire (FACT-hep)

8.6.3.1 Analysis of FACT-hep Scores

The total, domain, and individual question scores of the FACT-hep QoL instrument and their differences from baseline will be summarized at each time point by treatment group. The two treatment groups will be compared by applying a mixed linear model repeated measures analysis using a residual maximum likelihood estimation with the treatment, visit and the interaction between treatment and visit as factors, and the baseline score as a covariate. If the interaction term has a 2-sided p-value ≥ 0.15 then the model will be refitted without the interaction term. The Kenward-Roger approximation will be used to estimate the degrees of freedom. An unstructured covariance approach will be applied. If the fit of the unstructured covariance structure fails to converge, the following covariance structures will be tried in order until convergence is reached: Toeplitz with heterogeneity, autoregressive with heterogeneity, Toeplitz, and autoregressive. Means and least squares mean difference between treatment groups, along with a two-sided 95% CI and p-value for the difference between treatments will also be provided. This analysis will be performed on the mITT and PP populations.

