11.2 APPENDIX 2: STATISTICAL ANALYSIS AND PROGRAMMING DETAILS

The SAS procedure LIFETEST will be used in the Kaplan-Meier analyses. Patients who did not have an event will be censored.

The following code will be used:

```
proc lifetest data=all method=km alpha=0.05 outsurv=interval;  
    time aval*censr(1);  
    strata trtp;  
    id usbjid;  
run;
```

The SAS procedure PHREG will be used in the Cox regression analysis of time-to-event endpoints. Patients who did not have an event will be censored. The SAS method of discrete will be used to handle ties.

The SAS procedure MIXED will be used for mixed modeling. The following code will be used:

```
proc mixed method = reml;  
class BASE TRT VISIT SUBJID;  
model CH= BASE TRT VISIT TRT*VISIT /s ddfm=kr;  
repeated VISIT/type=UN subject=SUBJID;  
lsmeans TRT*VISIT /slice=VISIT diff alpha=0.05 cl;  
run;
```

where BASE is the baseline score, TRT is the assigned treatment, VISIT is the visit based on the window mapping, CH is the change from baseline.

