11.3 APPENDIX 3: FACT-hep Questionnaire Scoring Rules

FACT-hep Scoring Guidelines (Version 4)

Instructions:*

1. Record answers in "item response" column. If missing, mark with an X
2. Perform reversals as indicated, and sum individual items to obtain a score.
3. Multiply the sum of the item scores by the number of items in the subscale, then divide by the number of items answered. This produces the subscale score.
4. Add subscale scores to derive total scores (TOI & FACT-hep).
5. **The higher the score, the better the QOL.**

Subscale	Item Code	Reverse item?	Item response	Item Score
PHYSICAL WELL-BEING (PWB)	GP1	4	-	= _____
	GP2	4	-	= _____
	GP3	4	-	= _____
	GP4	4	-	= _____
	GP5	4	-	= _____
	GP6	4	-	= _____
	GP7	4	-	= _____
Score range: 0-28				
Sum individual item scores: _____				
Multiply by 7: _____				
Divide by number of items answered: _____				
=PWB subscale score				
SOCIAL/FAMILY WELL-BEING (SWB)	GS1	0	+	= _____
	GS2	0	+	= _____
	GS3	0	+	= _____
	GS4	0	+	= _____
	GS5	0	+	= _____
	GS6	0	+	= _____
	GS7	0	+	= _____
Score range: 0-28				
Sum individual item scores: _____				
Multiply by 7: _____				
Divide by number of items answered: _____				
=SWB subscale score				

EMOTIONAL WELL-BEING (EWB)	GE1	4	-	_____	= _____
	GE2	0	+	_____	= _____
	GE3	4	-	_____	= _____
	GE4	4	-	_____	= _____
Score range: 0-24	GE5	4	-	_____	= _____
	GE6	4	-	_____	= _____

Sum individual item scores: _____

Multiply by 6: _____

Divide by number of items answered: _____

=EWB subscale score

FUNCTIONAL WELL-BEING (FWB)	GF1	0	+	_____	= _____
	GF2	0	+	_____	= _____
	GF3	0	+	_____	= _____
	GF4	0	+	_____	= _____
Score range: 0-28	GF5	0	+	_____	= _____
	GF6	0	+	_____	= _____
	GF7	0	+	_____	= _____

Sum individual item scores: _____

Multiply by 7: _____

Divide by number of items answered: _____

=FWB subscale score

Subscale	Item Code	Reverse item?	Item response	Item Score
HEPATOBILIARY	C1	4	-	_____
CANCER	C2	4	-	_____
SUBSCALE (HCS)	C3	0	+	_____
	C4	0	+	_____
	C5	4	-	_____
Score range: 0-72	C6	0	+	_____
	Hep1	4	-	_____
	Cns7	4	-	_____
	Cx6	4	-	_____
	HI7	4	-	_____
	An7	0	+	_____
	Hep2	4	-	_____
	Hep3	4	-	_____
	Hep4	4	-	_____
	Hep5	4	-	_____
	Hep6	4	-	_____
	HN2	4	-	_____
	Hep8	4	-	_____

Sum individual item scores: _____

Multiply by 18: _____
Divide by number of items answered: _____
=HC Subscale score

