The simulations assumed that the effective sample size is 468 ($520*0.9$) if no adaptation occurs and 630 ($700*0.9$) in case that the total sample size is increased. The median survival time is assumed to be 10.7 months. The simulations for type I error were performed under the null hypothesis of the true hazard ratio 1. The total number of simulations is 1 million. All the simulations were conducted using East 6.4.1. Based on the simulations, 24881 trials out of 1 million are significant for the adaptive design (Adapt) and therefore the type I error level is 0.02488 which is below the nominal one-sided level 0.025. Note that the type I error for the group sequential design without sample size adaptation is 0.02533, which is slightly above the nominal one-sided level 0.025. This is due to the use of the normal approximation to the log rank statistics. Also, 0.02533 is still within three standard errors of Monte Carlo simulation. Table 1a shows the zonewise summary of the simulations under the null hypothesis for the group sequential design (GSD) and the adaptive design (Adapt). Table 1b shows the average sample size, events, accrual duration and study duration for the group sequential design and the adaptive design. The power performance were simulated for hazard ratio 0.754 and hazard ratio 0.781 and the results are summarized in Table 2a, Table 2b, Table 3a and Table 3b. The number of simulations for power performance is 100000. If the true hazard ratio is 0.754, the adaptive design with sample size increase provides 82% power compared to the group sequential design which has 80% power (Table 2a). If the trial lands in the promising zone, the power of the adaptive design is boosted to 89.6% as compared to 76.6% for the group sequential design (Table 2a). This gain of power comes with a cost of increased number of subjects and study duration. With the adaptive design, the average study duration is 93.9 months if the interim result of the trial falls in the promising zone (Table 2b). If the true hazard ratio is 0.781, then the power of the adaptive design is 71.2% which is about a 3 percentage point increase from 68.4% for the group sequential design. The conditional power given that the trial falls into the promising zone is boosted from 67.5% to 83% (Table 3a). Given that the trial lands into the promising zone, the average study duration of the adaptive design is 16.3 months longer (93.3 months) than the group sequential design (77 months) (Table 3b). If the trial falls out of the promising zone, the operating characteristics of the adaptive design is the same as the group sequential design since no changes are made to the trial conduct.

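### The FACT-Hep PROC MIXED code fits the baseline score as a category, not as the covariate that SAP 8.6.3.1 and the protocol specify

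*SAP*

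**What the plan says.** SAP Appendix 2 (11.2) introduces the PROC MIXED code as the code to be used, not as an example. Its CLASS statement is "class BASE TRT VISIT SUBJID". The MODEL statement contains BASE, TRT, VISIT and TRT*VISIT. The note beneath reads "where BASE is the baseline score", so BASE is the score itself and not a grouped version of it. The output line is "lsmeans TRT*VISIT /slice=VISIT diff alpha=0.05 cl", which gives treatment differences visit by visit.

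SAP 8.6.3.1 describes the same analysis in words. Treatment, visit and their interaction are factors; separately, it has "the baseline score as a covariate". The interaction is dropped if its p-value is 0.15 or more.

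The protocol describes the model twice. Section 10.2.3.2 has "the baseline score as a covariate and further adjusted for the interaction between baseline and visit". The synopsis has "a mixed linear model with baseline score and the relative time from baseline as covariates".

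FACT-Hep is the only mixed model in the visible SAP text, so the code can refer to nothing else.

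**The concern.** A CLASS variable in the MODEL statement gets one parameter per distinct value and no slope. The FACT-Hep total runs from 0 to 180, and the scoring rule for missing items ("Multiply the sum of the item scores by the number of items in the subscale, then divide by the number of items answered") produces non-integer totals. The number of baseline categories is therefore large, and many hold a single patient.

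A programmer cannot follow both Appendix 2 and 8.6.3.1. The two models can give different p-values for the same comparison, each defensible from the SAP. Following the code wastes information: a patient alone in a baseline category adds nothing to the between-patient part of the treatment comparison. The per-arm least squares means also change meaning, because LSMEANS by default weights every observed baseline level equally instead of evaluating at the mean baseline. The treatment difference itself is not shifted.

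Quality of life is a listed secondary endpoint (SAP 6.4.2). Whether a confirmatory test is affected cannot be told. The figure showing the testing hierarchy is not available, and the quality-of-life place in it may be the log-rank test of time to deterioration, which does not use this code.

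**Working it through.** **1. Text against code.**

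| Source | Role of baseline | Baseline-by-visit term |
|---|---|---|
| SAP Appendix 2 code | Categorical | No |
| SAP 8.6.3.1 | Covariate | No |
| Protocol 10.2.3.2 | Covariate | Yes |
| Protocol synopsis | Covariate, with time from baseline as a further covariate | No |

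No visible passage describes grouping the baseline score. The contradiction needs no arithmetic. The rest sizes its consequence; the plan has no figure to reproduce, because it states no power or SD for FACT-Hep.

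**2. Inputs for sizing.** From the documents: total score range 0–180 (SAP Appendix 3); n = 468, which is 520 × 0.9, from the survival simulations in SAP Appendix 5 ("The simulations assumed that the effective sample size is 468"); and n = 520 × 0.95 = 494 if only the ineligible 5% are removed. Assumed: baseline mean 130, SD 15–30, six visits, 85% retention per visit, within-patient correlation 0.6.

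**3. One visit, by hand.** With n patients and L baseline levels, randomization makes the expected variance ratio (categorical over continuous) about (n − 2)/(n − L). Simulating n = 468 gave L = 91 at SD 20 and L = 103 at SD 25.

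- L = 91: 466/377 = 1.24; simulated 1.23.
- L = 103: 466/365 = 1.28; simulated 1.28.
- L = 146 (SD 25, 10% of totals prorated): 466/322 = 1.45; simulated 1.45.

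For integer totals the SE ratio is then √1.23 = 1.11 to √1.28 = 1.13. Residual degrees of freedom fall from 465 to 376 and 364.

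**4. Repeated-measures model.** The BASE effect is shared across visits, so only the between-patient part of the variance is inflated. Generalized least squares variances under the step 2 assumptions, with 70–112 levels, give these SE ratios:

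| n, SD | Single visit | Visit-averaged | Common effect |
|---|---|---|---|
| 468, SD 15 | 1.047–1.075 | 1.099 | 1.102 |
| 468, SD 25 | 1.070–1.109 | 1.145 | 1.149 |
| 468, SD 30 | 1.077–1.120 | 1.159 | 1.163 |
| 494, SD 15 | 1.045–1.070 | 1.094 | 1.096 |
| 494, SD 30 | 1.076–1.118 | 1.156 | 1.160 |
| 494, SD 15, first visit complete | 1.038–1.059 | 1.079 | 1.081 |
| 468, SD 30, first visit complete | 1.067–1.105 | 1.139 | 1.142 |

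The single-visit column corresponds to the LSMEANS line. The common effect applies when the interaction is dropped under 8.6.3.1. These are small simulations; repeats put the upper ends at about 1.13 and 1.18.

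**5. Sensitivity (SE ratios).**

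- n = 468, SD 25, correlation 0.4–0.8, retention 75–95%: 1.044–1.149 single visit; 1.132–1.177 averaged or common.
- SD 25 with 10% of totals prorated (assumed): 1.097–1.176 and 1.199–1.237.
- Twelve visits: about 1.03–1.11 at single visits. n = 350: about 1.10–1.16.
- A 0–28 domain score (assumed SD 5.5): 1.014–1.031. A single 0–4 item: 1.002–1.004.

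**6. Power.** For a comparison with 80% power under the covariate model, power = Φ((1.960 + 0.842)/ratio − 1.960):

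- 1.04: 2.802/1.04 − 1.960 = 0.734, or 77%.
- 1.08: 0.634, or 74%.
- 1.12: 0.542, or 71%.
- 1.16: 0.456, or 68%.
- At the repeat-run upper ends, 1.13 gives 0.520 (70%) and 1.18 gives 0.415 (66%).

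**The case against.** The strongest reply is that the code is a skeleton and 8.6.3.1 governs. The code contains neither the refit without the interaction nor the fallback covariance structures that 8.6.3.1 requires, so it cannot be the whole analysis as printed. A programmer reconciling the two would find a clear model in the text. This lowers the chance of a wrong final analysis but does not remove the conflict, because Appendix 2 is worded as binding.

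Other points stand in part:

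- **Size.** The magnitude rests on assumed inputs, and n = 468 is a survival simulation size, not a count of FACT-Hep respondents. No power was planned for this endpoint, so the power figures are illustrative.
- **Impact.** The primary analysis is untouched, no confirmatory test is shown to be affected, and the cost is small for domain scores and trivial for items.
- **Declared changes.** SAP 5.2.4 is not visible, so it can only be said that the visible parts of 5.2 declare no change to this model.
- **Synopsis.** Time from baseline may be loose wording for visit.
- **Linearity.** A continuous baseline imposes a straight-line relation, which the categorical form does not. But the plan specifies the covariate.

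**Conclusion.** The concern holds. The prescribed code fits a different model from the one stated in SAP 8.6.3.1 and in both protocol descriptions. That conclusion rests on reading the documents and does not depend on the simulations.

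Following the code costs precision without biasing the treatment difference. For the total score, under the stated assumptions, the loss is about 4–12% in the SE at single visits and 8–16% for an averaged or common effect, with upper ends a point or two higher in repeat runs. It is larger if a noticeable share of totals is prorated. The matter should be fixed, but it does not threaten the trial's main conclusion.

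The missing baseline-by-visit term is a separate discrepancy between protocol and SAP. It also stands, subject to what the hidden SAP 5.2.4 contains.

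**What to change.** Change the statement in Appendix 2 to `class TRT VISIT SUBJID;` so that BASE is continuous. This is a one-word deletion and brings the code into line with SAP 8.6.3.1.

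Then settle the baseline-by-visit term. Either add it to the text of 8.6.3.1 and to the MODEL statement as BASE*VISIT, or record its omission in SAP 5.2 with a reason. The cost is one sentence and one model term, or one entry in 5.2. If the term is added, BASE must come out of CLASS first. Otherwise 70–112 levels over six visits would produce 70 × 6 = 420 to 112 × 6 = 672 baseline-by-visit cells. Align the synopsis wording with the choice.

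If the analysis has already been run, the sponsor should state which form of BASE produced the reported FACT-Hep results.

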11.3 APPENDIX 3: FACT-hep Questionnaire Scoring Rules

FACT-hep Scoring Guidelines (Version 4)

Instructions:*

1. Record answers in "item response" column. If missing, mark with an X
2. Perform reversals as indicated, and sum individual items to obtain a score.
3. Multiply the sum of the item scores by the number of items in the subscale, then divide by the number of items answered. This produces the subscale score.
4. Add subscale scores to derive total scores (TOI & FACT-hep).
5. **The higher the score, the better the QOL.**

Subscale	Item Code	Reverse item?	Item response	Item Score
PHYSICAL WELL-BEING (PWB)	GP1	4	-	= _____
	GP2	4	-	= _____
	GP3	4	-	= _____
	GP4	4	-	= _____
	GP5	4	-	= _____
	GP6	4	-	= _____
	GP7	4	-	= _____
Score range: 0-28				
Sum individual item scores: _____				
Multiply by 7: _____				
Divide by number of items answered: _____				
=PWB subscale score				
SOCIAL/FAMILY WELL-BEING (SWB)	GS1	0	+	= _____
	GS2	0	+	= _____
	GS3	0	+	= _____
	GS4	0	+	= _____
	GS5	0	+	= _____
	GS6	0	+	= _____
	GS7	0	+	= _____
Score range: 0-28				
Sum individual item scores: _____				
Multiply by 7: _____				
Divide by number of items answered: _____				
=SWB subscale score				

EMOTIONAL WELL-BEING (EWB)	GE1	4	-	_____	= _____
	GE2	0	+	_____	= _____
	GE3	4	-	_____	= _____
	GE4	4	-	_____	= _____
Score range: 0-24	GE5	4	-	_____	= _____
	GE6	4	-	_____	= _____

Sum individual item scores: _____

Multiply by 6: _____

Divide by number of items answered: _____

=EWB subscale score

FUNCTIONAL WELL-BEING (FWB)	GF1	0	+	_____	= _____
	GF2	0	+	_____	= _____
	GF3	0	+	_____	= _____
	GF4	0	+	_____	= _____
Score range: 0-28	GF5	0	+	_____	= _____
	GF6	0	+	_____	= _____
	GF7	0	+	_____	= _____

Sum individual item scores: _____

Multiply by 7: _____

Divide by number of items answered: _____

=FWB subscale score

Subscale	Item Code	Reverse item?	Item response	Item Score
HEPATOBILIARY	C1	4	-	_____
CANCER	C2	4	-	_____
SUBSCALE (HCS)	C3	0	+	_____
	C4	0	+	_____
	C5	4	-	_____
Score range: 0-72	C6	0	+	_____
	Hep1	4	-	_____
	Cns7	4	-	_____
	Cx6	4	-	_____
	HI7	4	-	_____
	An7	0	+	_____
	Hep2	4	-	_____
	Hep3	4	-	_____
	Hep4	4	-	_____
	Hep5	4	-	_____
	Hep6	4	-	_____
	HN2	4	-	_____
	Hep8	4	-	_____

Sum individual item scores: _____

Multiply by 18: _____
Divide by number of items answered: _____
=HC Subscale score

To derive a FACT-hep Trial Outcome Index (TOI):

Score range: 0-128

$$\frac{(\text{PWB score})}{(\text{PWB score})} + \frac{(\text{FWB score})}{(\text{FWB score})} + \frac{(\text{HCS score})}{(\text{HCS score})} = \text{FACT-hep TOI}$$

To Derive a FACT-hep total score:

Score range: 0-180

$$\frac{(\text{PWB score})}{(\text{PWB score})} + \frac{(\text{SWB score})}{(\text{SWB score})} + \frac{(\text{EWB score})}{(\text{EWB score})} + \frac{(\text{FWB score})}{(\text{FWB score})} + \frac{(\text{HCS score})}{(\text{HCS score})} = \text{FACT-hep Total score}$$

*For guidelines on handling missing data and scoring options, please refer to the Administration and Scoring Guidelines in the manual or on-line at www.facit.org.

11.4 APPENDIX 4: Definition and Derivation of Subsequent HCC Therapy

A patient is considered to have received ‘subsequent HCC therapy’, after the protocol required treatments, if they had

- a subsequent systemic anti-cancer treatment (excluding sorafenib), and/or
- a non-protocol liver directed therapy (excluding ablation/surgery)

Subsequent systemic anti-cancer treatment will be identified using all non-sorafenib records from the “Best Available Care - Post Treatment Discontinuation – Medication” eCRF page. Note that all records on the “Best Available Care - Post Treatment Discontinuation – Medication” eCRF page are expected to be systemic anti-cancer treatments for HCC after data cleaning has been completed.

Non-protocol liver directed therapy will be identified using all records (except ablation/surgery) from “Additional Procedures” eCRF page. This eCRF page captures any procedures relating to liver directed therapies outside the study protocol, such as liver ablation, liver surgery, liver external beam radiation therapy, SIRT with rhenium, SIRT with Y90 (including TheraSphere for patients randomized to control group), TACE, and transarterial embolization (TAE). The free text field “procedure term” will be reviewed and categorized by physician, which will be finalized prior to the database hard lock. Procedures identified as liver ablation and liver surgery by physician’s review will not be considered as subsequent HCC therapy.

Notes:

- Treatments recorded on the “Resection / HCC Stage Migration” eCRF page will not be considered as subsequent HCC therapy, since these treatments are delivered to patients who had a downstaging of disease and represents a population possible to have better outcomes and important to follow-up.
- TheraSphere treatment/retreatment for patients randomized to TheraSphere group, recorded on the “TheraSphere Doses Administered” eCRF page, are study treatment per protocol, so will not be considered as subsequent HCC therapy.

[figure not shown]
**11.5 APPENDIX 5: Statistical Details of the Adaptive Design for Protocol TS-103
STOP-HCC**

Statistical Details of the Adaptive Design

1 Design Overview

This study uses an adaptive group sequential design with two interim analyses and one final analysis. The efficacy stopping boundaries will be based on the rho family error spending function with the parameter value $\rho = 1.5$. An assessment of futility at the two interim analyses, based on conditional power, was included in the study design. However, it was decided by the Sponsor before the first interim analysis was performed, that the futility assessment would not be performed, primarily because patient recruitment was faster than expected towards the latter part of the study, such that all patients for the original sample size had already been randomized. A total of 417 events are planned based on providing more than 80% power to detect a hazard ratio of 0.754 with the group sequential design. The first interim analysis is planned at 45% (188 events) information time and the second interim analysis is planned at 60% (250 events) information time. However if the true hazard ratio is 0.781 which is larger than 0.754 but is still considered as a clinically meaningful improvement, the study will be at risk of being underpowered. Therefore a promising zone approach as in Mehta and Pocock (2011) will be employed at the second interim analysis to increase the total number of events. The design is depicted by the following flow chart. More specifically, the first interim analysis is planned to be performed when 188 overall survival (OS) events are observed at which the trial may be stopped for overwhelming efficacy at the first interim analysis time if the observed Z-score statistic crosses the efficacy boundary 2.430. If at the first interim look the study is not stopped for efficacy, the trial will continue and the second interim analysis is planned to be performed when 250 OS events are observed. At the second interim analysis, the trial will be terminated for efficacy (if efficacy boundary 2.429 is crossed). If the trial is not stopped for efficacy, the conditional power given the observed trend will be calculated. If the conditional power of the trial at the second interim analysis falls in the unfavorable zone with conditional power less than 42% or in the favorable zone with conditional power larger than 80%, the trial will continue as planned and the final analysis will be performed when 417 OS events are observed. If the trial falls in the promising zone with conditional power between 42% and 80%, the total number of OS events required will be increased and the final analysis will occur when 564 OS events are observed. The final analysis will be performed by comparing the Z-score statistic to the original group sequential boundary 2.093. The efficacy boundary would be re-calculated using the rho family spending function ($\rho=1.5$) if the actual interim look did not occur at exactly the planned number of events.

Figure 1: Design Schema

2 Justification of Type I Error

This adaptive design with sample size re-estimation described in Section 1 strongly controls type I error. The type I error control follows from a similar argument as in Mehta and Pocock (2011) or Gao et al (2008). The essential idea behind it is the so-called Muller and Shaffer principle as proposed in Muller and Shaffer (2001). More specifically, let Z_2 and Z_3 denote the Z-score based on a log rank statistic using the cumulative data available at the second look and the last look for the three-look group sequential design with the initial planned 417 OS events without sample size adaptation. Let c_3 be the efficacy boundary of the group sequential design at the last look. Let Z_3^* be the Z-score based on all cumulative data available at the final look for the adaptive design depicted by Figure 1, where the total number of events will remain at 417 if the trial at the second look lands in the unfavorable zone with conditional power (CP) <42% or in the favorable zone with CP $\geq 80\%$, otherwise the total number of events

will be increased in a fixed amount to 564 if the trial lands into the promising zone with conditional power between 42% to 80%. The adaptive design in Figure 1 will test the null hypothesis by comparing Z_3^* to the group sequential boundary c_3 at the final look. The Muller and Shaffer (2001) principle says that the overall type I error will be controlled if the final test in the adaptive design preserves the conditional type I error of the group sequential design. The conditional type I error for the group sequential design is $P_0(Z_3 > c_3 | Z_2 = z_2)$ and the conditional type I error for the adaptive design is $P_0(Z_3^* > c_3 | Z_2 = z_2)$. Therefore to show that the type I error for the adaptive design in Figure 1 is strongly controlled, it is sufficient to show that

$$P_0(Z_3^* > c_3 | Z_2 = z_2) \leq P_0(Z_3 > c_3 | Z_2 = z_2) \quad (1)$$

for any z_2 which lands into one of the three zones: unfavorable, favorable and promising.

If the conditional power of the trial at the second interim analysis lands in the unfavorable zone ($CP_2 < 0.42$) or favorable zone ($CP_2 \geq 0.8$), the number of events is not increased which implies Z_3^* is the same as Z_3 . Therefore $P_0(Z_3^* > c_3 | Z_2 = z_2) = P_0(Z_3 > c_3 | Z_2 = z_2)$. On the other hand, if the trial lands into the promising zone with conditional power between 0.42 and 0.8, the total number of events will be increased to 564. Let c_3^* be the adjusted boundary such that the conditional type I error is preserved i.e. $P_0(Z_3^* > c_3^* | Z_2 = z_2) = P_0(Z_3 > c_3 | Z_2 = z_2)$. In the Appendix, we have shown that $c_3^* < c_3$ for any z_2 in the promising zone as seen from Figure 2 which implies that $P_0(Z_3^* > c_3 | Z_2 = z_2) \leq P_0(Z_3^* > c_3^* | Z_2 = z_2)$. Therefore $P_0(Z_3^* > c_3 | Z_2 = z_2) \leq P_0(Z_3 > c_3 | Z_2 = z_2)$.

3 Simulations

This section summarizes the operating characteristics of the adaptive design with the option to increase events and sample size (the design described in Section 1) at interim analysis time compared to the group sequential design. Two interim analyses are planned and the efficacy boundaries are derived based on the ρ family error spending function with $\rho = 1.5$. The first interim analysis is planned at 188 overall survival events and the second interim at 250 events. At the second interim analysis, the conditional power will be computed. If the conditional power is $< 42\%$ or $\geq 80\%$, the trial will continue and the final analysis will be performed when 417 events are observed. On the other hand, if the conditional power of the trial is between 42% and 80%, the total number of events will be increased to 564 uniformly (as shown in Figure 1) based on providing 80% power to detect an improvement in median OS from 10.7 to 13.7 months using a log rank test with a final two-sided alpha of 0.0363. It is planned to enroll 520 subjects in 60 months with additional 18 months follow-up. This includes an adjustment to take account of an assumed 5% of patients who will be lost to follow-up and for whom a date of death is not recorded, and an assumed additional 5% of patients who will be erroneously randomized because they did not meet the eligibility criteria at randomization. If the total number of events is increased to 564, it is planned to enroll 700 subjects in 66 months with

additional 18 month follow-up. Similarly, this includes an adjustment to take account of an assumed 5% of patients who will be lost to follow-up and for whom a date of death is not recorded, and an assumed additional 5% of patients who will be erroneously randomized because they did not meet the eligibility criteria at randomization.

The simulations assumed that the effective sample size is 468 ($520*0.9$) if no adaptation occurs and 630 ($700*0.9$) in case that the total sample size is increased. The median survival time is assumed to be 10.7 months. The simulations for type I error were performed under the null hypothesis of the true hazard ratio 1. The total number of simulations is 1 million. All the simulations were conducted using East 6.4.1. Based on the simulations, 24881 trials out of 1 million are significant for the adaptive design (Adapt) and therefore the type I error level is 0.02488 which is below the nominal one-sided level 0.025. Note that the type I error for the group sequential design without sample size adaptation is 0.02533, which is slightly above the nominal one-sided level 0.025. This is due to the use of the normal approximation to the log rank statistics. Also, 0.02533 is still within three standard errors of Monte Carlo simulation. Table 1a shows the zonewise summary of the simulations under the null hypothesis for the group sequential design (GSD) and the adaptive design (Adapt). Table 1b shows the average sample size, events, accrual duration and study duration for the group sequential design and the adaptive design. The power performance were simulated for hazard ratio 0.754 and hazard ratio 0.781 and the results are summarized in Table 2a, Table 2b, Table 3a and Table 3b. The number of simulations for power performance is 100000. If the true hazard ratio is 0.754, the adaptive design with sample size increase provides 82% power compared to the group sequential design which has 80% power (Table 2a). If the trial lands in the promising zone, the power of the adaptive design is boosted to 89.6% as compared to 76.6% for the group sequential design (Table 2a). This gain of power comes with a cost of increased number of subjects and study duration. With the adaptive design, the average study duration is 93.9 months if the interim result of the trial falls in the promising zone (Table 2b). If the true hazard ratio is 0.781, then the power of the adaptive design is 71.2% which is about a 3 percentage point increase from 68.4% for the group sequential design. The conditional power given that the trial falls into the promising zone is boosted from 67.5% to 83% (Table 3a). Given that the trial lands into the promising zone, the average study duration of the adaptive design is 16.3 months longer (93.3 months) than the group sequential design (77 months) (Table 3b). If the trial falls out of the promising zone, the operating characteristics of the adaptive design is the same as the group sequential design since no changes are made to the trial conduct.

Table 1a: Simulation for Type I Error under Hazard Ratio 1

Zone	Prob. of Entering Each Zone (%)	Power (%)	
		GSD	Adapt
Unfavorable	93.4%	0.6%	0.6%
Promising	4.2%	12.5%	10.5%
Favorable	1.2%	26.7%	27.2%
Efficacy	1.2%	100%	100%
All Trials	100%	2.533%	2.488%

Table 1b: Average Sample Size, Events, and Durations under Hazard Ratio 1

Zone	Average Sample Size		Average Number of Events		Average Accrual Duration (months)		Average Study Duration (months)	
	GSD	Adapt	GSD	Adapt	GSD	Adapt	GSD	Adapt
Unfavorable	467	467	417	417	59.9	59.9	73	73
Promising	467	629	417	563	59.9	80.6	73	89.8
Favorable	467	467	417	417	59.9	59.9	73	73
Efficacy	321	321	209	210	41	41	41	41
All Trials	465	472	415	421	59.6	61	72.7	73.4

Table 2a: Power under Hazard Ratio 0.754

Zone	Prob. of Entering Each Zone (%)	Power (%)	
		GSD	Adapt
Unfavorable	23.6%	39%	39%
Promising	17.7%	76.6%	89.6%
Favorable	13.3%	89%	88.8%
Efficacy	45.3%	100%	100%
All Trials	100%	80%	82%

Table 2b: Average Sample Size, Events, and Durations under Hazard Ratio 0.754

Zone	Average Sample Size		Average Number of Events		Average Accrual Duration (months)		Average Study Duration (months)	
	GSD	Adapt	GSD	Adapt	GSD	Adapt	GSD	Adapt
Unfavorable	467	467	417	417	59.9	59.9	77.5	77.5
Promising	467	629	417	563	59.9	80.6	77.7	93.9
Favorable	467	467	417	417	59.9	59.9	77.7	77.7
Efficacy	334	335	208	208	42.7	42.8	42.8	42.9
All Trials	407	435	322	347	52	55.7	62	64.6

Table 3a: Power under Hazard Ratio 0.781

Zone	Prob. of Entering Each Zone (%)	Power (%)	
		GSD	Adaptive
Unfavorable	33.2%	30%	29.5%
Promising	19.2%	67.5%	83%
Favorable	12.8%	84%	84%
Efficacy	34.8%	100%	100%
All Trials	100%	68.4%	71.2%

Table 3b: Average Sample Size, Events, and Durations under Hazard Ratio 0.764

Zone	Average Sample Size		Average Number of Events		Average Accrual Duration (months)		Average Study Duration (months)	
	GSD	Adapt	GSD	Adapt	GSD	Adapt	GSD	Adapt
Unfavorable	467	467	417	417	59.9	59.9	76.9	76.9
Promising	467	629	417	563	59.9	80.6	77	93.3
Favorable	467	467	417	417	59.9	59.9	77	77
Efficacy	334	334	209	209	42.7	42.7	42.8	42.8
All Trials	421	451	345	372	53.9	57.8	65	68

